## 10.2.4. The percentage of patients who require rescue therapy (i.e. receive any alternative IV antihypertensive drug) at any time during study drug treatment period or discontinuation due to adverse events

The percentage of patients achieving this endpoint will be calculated using the number of patients achieving the endpoint divided by total number of patients, and multiplied by 100. Two-tailed 95% CIs will be computed for these percentages.

Number and percent of patients achieving the endpoints along with the calculated 95% CI will be presented.

# 10.2.5. Percent change in SBP from baseline at each time point during the 30 minutes of clevidipine infusion, at each hour after the first 30 minutes of clevidipine infusion up to the cessation of infusion, and over the first 12 hours post study drug termination

Blood pressure will be measured every 1.5 minutes for the first 30 minutes of infusion, every 10 minutes in the next hour, every 30 minutes for the next 2 hours then every hour until the study drug is terminated or maximum 96 hours from initiation of study drug is reached, whichever is earlier. Blood pressure will also be measured just prior to each PK blood draw and each dose adjustment, as well as every 1.5 minutes for 15 minutes after the dose adjustment. After termination of the clevidipine infusion, blood pressure will be taken every 15 minutes for the first hour, then every hour for a maximum of 12 hours.

Descriptive statistics on changes and percent changes from baseline in SBP will be summarized at each specified timepoint. A graph will be presented on percent change in SBP during the first 30 minutes after initiation of study medication by age cohort.

Individual patient graphs will present SBP across all timepoints along with the study drug dose levels in mg/h.

### 10.2.6. Percent change from baseline in heart rate during the first 30 minutes of clevidipine infusion and the rest of the treatment period

Heart rate (HR) will be measured every 1.5 minutes for the first 30 minutes of study drug infusion, every 10 minutes in the next hour, every 30 minutes for the next 2 hours then every hour until the study drug is terminated or maximum 96 hours from initiation of study drug is reached whichever is earlier.

Descriptive statistics on changes and percent changes from baseline in HR will be summarized at each specified timepoint within 30 minutes of clevidipine infusion. A graph will be made of percent change in HR during the first 30 minutes after initiation of study medication by age cohort.

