2.2. SECONDARY OBJECTIVES

To evaluate additional efficacy, safety and dosing parameters associated with IV infusion of clevidipine for BP management in pediatric patients in the perioperative setting.

Additional assessments will include the percentage change in SBP from baseline at each time point during the first 30 minutes following initiation of clevidipine infusion.

Evaluation of efficacy after the initial 30 minute infusion period will include the percent change from baseline in SBP at each hour after the first 30 minutes of clevidipine infusion up to the cessation of infusion and the percentage of patients in whom the SBP is within target range at each hour after the first 30 minutes of clevidipine infusion.

Safety data will include:

- The percentage of patients who reach the initial prespecified target SBP range without falling below the lower limit of the prespecified target range during the first 30 minutes of clevidipine infusion
- The percentage of patients in whom the SBP falls below the lower limit of the prespecified target range at any time during the first 30 minutes and at any time during the entire study drug treatment period
- The percent change from baseline in heart rate during the first 30 minutes of clevidipine infusion and during the rest of the treatment period; and
- The percentage of patients who require rescue therapy at any time during study drug treatment period

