3.4. SECONDARY ENDPOINT(S)

The secondary endpoints of this trial are:

- The percentage of patients who reach the initial prespecified target SBP range without falling below the lower limit of the prespecified target range during the first 30 minutes of clevidipine infusion
- The percentage of patients in whom the SBP falls below the lower limit of the prespecified target range at any time during the first 30 minutes and at any time during the entire study drug treatment period
- Percentage change in SBP from baseline at each time point during the 30 minutes of clevidipine infusion
- Percent change from baseline in SBP at each hour after the first 30 minutes of clevidipine infusion up to the cessation of infusion
- The percentage of patients in whom the SBP is within target range at each hour after the first 30 minute of clevidipine infusion
- Percent change from baseline in heart rate during the first 30 minutes of clevidipine infusion and the rest of the treatment period
- Percentage of patients who require rescue therapy (i.e., receive any alternative IV antihypertensive drug) at any time during study drug treatment period, or discontinuation due to adverse events

Percent change from baseline in SBP over the first 12 hours post study drug termination

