10.3.2.2. Secondary Efficacy Endpoints

The secondary efficacy endpoints are:

• The percentage of patients who reach the initial prespecified target SBP range without falling below the lower limit of the prespecified target range during the first 30 minutes of clevidipine infusion

- The percentage of patients in whom the SBP falls below the lower limit of the pre specified target range at any time during the first 30 minutes and at any time during the entire study drug treatment period
- The percentage of patients in whom the SBP is within target range at each hour after the first 30 minute of clevidipine infusion
- The percentage of patients who require rescue therapy (i.e., receive any alternative IV antihypertensive drug) at any time during study drug treatment period or discontinuation due to adverse events.

The percentage of patients reaching each endpoint above will be calculated for overall and within each cohort using the number of ITT patients achieving the endpoint divided by the number of total ITT patients, and multiplied by 100.

Number and percent of patients achieving each endpoint during the first 30 minutes along with the calculated 95% confidence interval will be presented.

- Percent change in SBP from baseline at each time point during the 30 minutes of clevidipine infusion
- Percent change from baseline in SBP at each hour after the first 30 minutes of clevidipine infusion up to the cessation of infusion
- Percent change from baseline in SBP over the first 12 hours post study drug termination
- Percent change from baseline in heart rate during the first 30 minutes of clevidipine infusion and the rest of the treatment period

Percent change from baseline at each time point specified in above endpoints will be calculated for each ITT patient.

Descriptive statistics will be presented for overall and by cohort.

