### 18. CHANGES TO ANALYSES SPECIFIED IN THE PROTOCOL

In Protocol Section 10.3.3.3, it was stated to analyze vital signs at each collection time point. In this study, the only vital signs that are collected are SBP, DBP and HR which are already analyzed as individual efficacy endpoint hence there is no additional analysis on vital signs performed.

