### 20. APPENDIX

#### 20.1. TIME WINDOWS

### 20.1.1. Visit windows for hemodynamic data (SBP, DBP and HR)

Hemodynamic data (SBP, DBP and HR) will be presented at every 1.5 minutes within 30 minutes of study drug infusion, at every 30 minutes for the next 3 hours, at every hour thereafter till the cessation of infusion and over 12 hours post study treatment. The time window is 30 seconds for 1.5 minutes presentation, 10 minutes for every 30 minutes presentation and 30 minutes for hourly presentation.

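### SAP 10.2.6 limits the heart-rate change statistics to the first 30 minutes, although the endpoint runs through treatment, so SAP 18's reason for dropping the vital-sign summary fails for later heart rate

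*SAP*

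**What the plan says.** **Endpoint.** Protocol Section 3.4 lists the secondary endpoint as "Percent change from baseline in heart rate during the first 30 minutes of clevidipine infusion and the rest of the treatment period". Protocol Section 2.2 places the same measure, again including the rest of treatment, in its list of safety data. For the percent-change endpoints, Protocol Section 10.3.2.2 states: "Percent change from baseline at each time point specified in above endpoints will be calculated for each ITT patient".

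**Stated HR analysis.** The heading of SAP Section 10.2.6 repeats the full endpoint, and its first paragraph gives the HR recording schedule up to 96 hours. The analysis text then says that descriptive statistics on change and percent change in HR "will be summarized at each specified timepoint within 30 minutes of clevidipine infusion". The one graph has the same limit: "A graph will be made of percent change in HR during the first 30 minutes after initiation of study medication by age cohort".

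**Vital signs.** Protocol Section 10.3.3.3 asks for change and percent change in vital signs at every scheduled time point. SAP Section 18 removes this. It reasons that SBP, DBP and HR are the only vital signs collected and that each is already analysed for efficacy, "hence there is no additional analysis on vital signs performed".

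**Appendix.** SAP Section 20.1.1 begins "Hemodynamic data (SBP, DBP and HR) will be presented at every 1.5 minutes within 30 minutes of study drug infusion". The same sentence continues half-hourly over the following 3 hours, then hourly to the end of infusion, then over the 12 hours after treatment.

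**The concern.** Part of a named secondary endpoint has no stated change-from-baseline analysis. The protocol's separate vital-sign summary would have supplied one, but SAP Section 18 removes it on the assumption that the efficacy section already does the job. For HR after 30 minutes, Section 10.2.6 as written does not. SAP Section 11 covers only adverse events and laboratory parameters, so no safety section fills the gap. Section 18 also does not list the shortened HR summary as a departure from the protocol.

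HR change is safety information in this trial. Protocol Section 5.2.3 permits beta-blockers for reflex tachycardia, so the protocol anticipates that response. Protocol Section 1.2.1 reports a reflex HR rise in conscious animals but no HR effect in anesthetized ones, and Protocol Section 6 starts the infusion under stable anesthesia. The first 30 minutes may therefore be the less informative part of the HR record. That is an inference from animal data only, and Protocol Section 5.1.1 says the reflex was not seen in post-cardiac-surgery patients. The point does not depend on it.

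**Working it through.** The plan gives no figure to reproduce here. The check compares the relevant sections and then counts scheduled readings.

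**1. Time coverage of the stated change statistics**

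| Measure | SAP section | Coverage |
|---|---|---|
| SBP | 10.2.5 | every specified time point: first 30 minutes, later infusion, 12 hours after |
| DBP, MAP | 10.3 | percent change over time, no limit stated |
| HR | 10.2.6 heading | first 30 minutes and the rest of treatment |
| HR | 10.2.6 statistics and graph | first 30 minutes only |
| HR | 20.1.1 | presented to the end of infusion and 12 hours after; no statistic named |

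The SBP and HR statistics sentences are built alike, but only the HR one carries the 30-minute limit. Of the three vital signs named in SAP Section 18, HR is the only one whose stated efficacy analysis stops there.

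**2. Scheduled on-treatment HR readings.** The schedule is in the first paragraph of SAP 10.2.6. Extra readings around dose changes and PK draws are left out.

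- First 30 minutes, every 1.5 minutes: 30 / 1.5 = 20.
- Next hour, every 10 minutes: 60 / 10 = 6 (to 1.5 hours).
- Next 2 hours, every 30 minutes: 120 / 30 = 4 (to 3.5 hours).
- Hourly thereafter: at 4.5, 5.5, ... hours. Up to 96 hours the last is at 95.5, giving 92.

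| Infusion duration | Readings after 30 minutes | All readings | Share after 30 minutes |
|---|---|---|---|
| 1 h | 3 | 23 | 13% |
| 4 h | 6 + 4 = 10 | 30 | 33% |
| 24 h | 6 + 4 + 20 = 30 | 50 | 60% |
| 96 h | 6 + 4 + 92 = 102 | 122 | 84% |

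Ninety-six hours is the protocol maximum. The documents give no expected distribution of infusion durations, so the shorter ones are illustrations. For an infusion of exactly 30 minutes, no on-treatment reading is missed.

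**3. What Appendix 20.1.1 already provides.** For a 96-hour infusion its grid has 6 half-hourly points (180 / 30) and 92 hourly points after the first 30 minutes: 6 + 92 = 98. The time points and windows for a later HR summary therefore exist. What is missing is an instruction to compute change and percent change at them.

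**The case against.** The strongest reply is that later HR will be shown anyway. Appendix 20.1.1 names HR and says it will be presented through the infusion and for 12 hours after. SAP Section 4 promises that all data will be summarised overall and by age cohort, with listings of everything in the eCRF. SAP Section 14.2 summarises HR when the target range is changed, which can only be after the first 30 minutes. The 10.2.6 heading and schedule also suggest a drafting slip and not a decision, and the study is descriptive with no formal testing.

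Much of this stands, and it rules out several stronger readings. A reader might infer that HR after 30 minutes would go unreported; Appendix 20.1.1 says otherwise. A reader might infer that 10.2.6 deliberately excludes later HR; it contains no exclusion, only a statistics sentence narrower than its heading. A reader might size the gap by elapsed time, since 0.5 h / 96 h = 0.5%; that exaggerates it, because readings are densest in the first 30 minutes and 96 hours is the maximum.

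A reader might also count post-infusion HR as a shortfall against the HR endpoint. The endpoint ends with treatment, and only SBP has a separate 12-hour post-infusion endpoint. Protocol Section 10.2.3 does run the last treatment phase on to the 12-hour follow-up, but it also counts those hours as follow-up. Post-infusion HR is in question only through Protocol 10.3.3.3 and SAP 18.

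What the reply does not supply is the statistic. Neither Appendix 20.1.1 nor Section 4 calls for change or percent change in HR, and Section 14.2 covers HR values at selected moments only.

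**Conclusion.** The point holds as an internal inconsistency with a practical consequence. SAP 10.2.6 conflicts with its own heading, with the endpoint in Protocol 2.2, 3.4 and 10.3.2.2, and with the presentation grid in Appendix 20.1.1. As written, no section requires change or percent change in HR after the first 30 minutes. The reason in SAP 18 for dropping the Protocol 10.3.3.3 summary therefore fails for HR after 30 minutes and after infusion. It does not fail for SBP or DBP, which are covered over time.

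The share of scheduled on-treatment readings affected runs from 13% at 1 hour to 84% at 96 hours. The share that applies depends on infusion durations the documents do not predict. The gap concerns time coverage alone: SAP 10.2 already runs all secondary analyses in both the ITT and safety populations. Nothing in data collection is at fault. This should be corrected, but it does not threaten the primary analysis.

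**What to change.** 1. In SAP 10.2.6, replace the 30-minute limit in the statistics sentence with the Appendix 20.1.1 time points from initiation through the end of infusion, for both change and percent change in HR. The 30-minute graph can stay.
2. Add the same HR summary for the 12 hours after infusion, identified as meeting Protocol 10.3.3.3 and not as part of the HR endpoint.
3. In SAP 18, point to these tables as the reason no separate vital-sign analysis is needed.

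The analysis populations need no change. If the sponsor does intend to stop at 30 minutes, Section 18 should list that as a departure from the protocol and give the reason; this is the weaker option, because it leaves part of the endpoint unanalysed.

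The cost is SAP wording and a few more rows in an existing table. The readings are already collected and the windows already defined.

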### 10.3. OTHER EFFICACY ANALYSIS

The following endpoint will be summarized and presented:

- Percent change from baseline in diastolic blood pressure (DBP) over time
- Percent change from baseline in mean arterial pressure (MAP) over time

### 11. SAFETY ANALYSES

Safety of a prolonged infusion of clevidipine up to 96 hours will be assessed according to adverse events (AE)/serious adverse events (SAE) up to 7 (+ 1) days following study treatment termination, and clinical laboratory parameters.

Unless otherwise specified, all safety analyses will use the defined safety population.

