, **CCI**, up to the maximum dose of **CCI** every 1.5 minutes until a SBP within the prespecified target range is reached. The initial dose for children, infant and toddler cohorts and the subsequent up-titration doses will be determined after an interim analysis of data from the preceding cohorts. As the blood pressure approaches the desired range, dosing may be increased by less than doubling, and the time between dose adjustments may be lengthened to greater than 1.5 minutes. If the target SBP range is achieved at any of the titration doses, that rate may be maintained for up to 96 hours to maintain the BP, or titrated up or down as necessary to maintain SBP within the target range. Clevidipine infusion may be terminated at any time for safety reasons. Per protocol dosing reflects clinical experience to date, additional clinical utility is typically not observed for doses above

Dosing in the remaining cohorts will be the same as adolescents unless information obtained from the previous cohorts suggests the need for modification of the starting dose and/or the incremental titration schema.

During the initial 30 minutes of the treatment period, clevidipine should be administered continuously as monotherapy. The use of an alternative IV antihypertensive agent is discouraged and should be limited to situations where it is medically necessary to maintain patient safety. If the desired BP control effect is not attained using the maximum dose of clevidipine, rescue therapy with the use of an alternative IV antihypertensive agent should be implemented.

After the first 30-minute treatment period, it may be necessary to alter the desired SBP target range over the course of the remaining treatment period. Any changes in the target range will be captured in the eCRF.

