3.3. PRIMARY ENDPOINT(S)

The primary endpoint(s) of this trial are:

- Median time and dose to attain the initial prespecified target SBP range (minimum of 20 mmHg and a maximum of 40 mmHg apart) during the first 30 minutes of clevidipine infusion
- Percentage of patients achieving the initial prespecified target SBP range during the first 30 minutes of clevidipine infusion
- Pharmacokinetic variables (half-life, area under the curve [AUC], volume of distribution, clearance) established by sparse population methodology
- Pharmacodynamic variables (relationship between change from baseline in SBP vs. blood concentration and infusion rate)
- Safety of a prolonged infusion of clevidipine (up to 96 hours) assessed according to clinical laboratory parameters, adverse events and serious adverse events (SAEs) will be assessed from time of consent through 7 days following termination of study drug infusion

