4.2. INCLUSION CRITERIA

Patients may be included in the study if they meet all of the following criteria:

- 1. Patient must be less than 18 years
- 2. Written informed consent obtained before initiation of any study-related procedures
- 3. The enrolling physician determines that patient will likely require a 15% reduction in BP during the perioperative course
- 4. Intra-arterial line available for blood pressure monitoring
- 5. Surgical procedure requiring at minimum 1 hour of anesthesia, in which IV antihypertensive therapy to control BP for at least 30 minutes is anticipated

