### 3.1. SAFETY POPULATION

The safety population consists of all patients who are dosed with any study drug. This will be the primary population used for the safety analyses.

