### 11.1. ADVERSE EVENTS

The Medical Dictionary for Regulatory Activities (MedDRA) will be used for coding AEs. An AE (classified as preferred term) occurring after initiation of study drug will be counted as a treatment emergent AE (TEAE) either if it is not present at baseline or if it is present at baseline but increased in severity after initiation of study drug. If more than one AE with the same preferred term was reported pre-baseline, then the report with the greatest intensity is used as the benchmark for comparison to post-baseline reports of events with that preferred term.

The number (percentage) of patients reporting TEAEs for each preferred term will be tabulated by system-organ class, by system-organ class and severity, and by system-organ class and relationship to study drug. If more than one event occurred with the same preferred term for the same patient, the patient will be counted only once for that preferred term using the most severe or related occurrence for the summary by severity, or relationship to study drug, respectively. An individual patient will be counted only once for any specific preferred term regardless of the number of times that preferred term occurred for that patient.

The incidence of SAEs and AEs leading to discontinuation of study drug will be summarized separately by system-organ class, preferred term for the safety population.

Listings will be presented for patients with SAEs/AEs leading to a discontinuation or death.

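### A primary endpoint is the safety of prolonged infusion, but the planned AE and SAE percentages are not linked to how long patients were infused

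*SAP*

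**What the plan says.** **Endpoint.** Protocol 3.3 lists among the primary endpoints "Safety of a prolonged infusion of clevidipine (up to 96 hours) assessed according to clinical laboratory parameters, adverse events and serious adverse events (SAEs". SAP 11 repeats it: "Safety of a prolonged infusion of clevidipine up to 96 hours will be assessed according to adverse events (AE)/serious adverse events (SAE".

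**Exposure.** Protocol 4.2 asks only for a surgical procedure "in which IV antihypertensive therapy to control BP for at least 30 minutes is anticipated". Ninety-six hours is a permitted maximum: once the target range is reached, "that rate may be maintained for up to 96 hours to maintain the BP" (Protocol 3.1). The same section allows the infusion to be stopped at any time for safety. Neither document defines prolonged for this trial, and neither requires a number of patients, overall or per cohort, with more than 30 minutes of infusion. The sample size (Protocol 10.1, SAP 16) rests on the proportion reaching target within 30 minutes, with a separate remark on PK/PD adequacy.

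**Analysis.** SAP 3.1 states: "The safety population consists of all patients who are dosed with any study drug". SAP 11 makes this the default population for safety. Under SAP 11.1, "The number (percentage) of patients reporting TEAEs for each preferred term will be tabulated by system-organ class", and also by severity and by relationship. SAEs and AEs leading to discontinuation are summarised separately in the same population. SAP 4 splits all summaries by age cohort, and SAP 13 adds pre-existing hypertension where numbers allow. SAP 8 summarises overall and on-drug infusion duration, but no AE table uses either.

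**The concern.** The endpoint asks what happens during and after a long infusion. The planned percentages answer a different question: how often events occur after any infusion. A 35-minute intra-operative infusion and a 90-hour infusion carry equal weight in the same denominator.

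The documents themselves treat duration as relevant. Protocol 1.2.1 relates most of the animal toxicity findings to dose, duration or both. Protocol 3.1 singles out prolonged infusions for rebound-hypertension monitoring.

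The risk is one of interpretation. A low AE percentage over about 80 children could be read as reassurance about multi-day use when few of them had it, and no planned AE table would show that.

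**Working it through.** **1. The plan's own figure.** Protocol 10.1 and SAP 16 give a 95% precision of ±6.6% at 90% and ±7.8% at 85% for n = 80. The half-width is 1.96 × √(p(1−p)/80):
- p = 0.90: 1.96 × √(0.09/80) = 6.57%
- p = 0.85: 1.96 × √(0.1275/80) = 7.82%

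Both reproduce. They concern the 30-minute efficacy proportion and say nothing about safety exposure.

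**2. Inputs for the safety question.**
- N = 80, 20 per cohort (Protocol 10.1).
- The number n with a prolonged infusion is not in the documents. Assumed: 10%, 25% or 50% of 80, that is 8, 20 or 40 patients.
- Event risks are assumed, for illustration only.

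**3. What n patients can show.**
- Upper limit with zero events, one-sided 95%: 1 − 0.05^(1/n). The two-sided exact version is 1 − 0.025^(1/n).
- Chance of at least one case of an event with 5% risk: 1 − 0.95^n.

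| Patients with prolonged infusion | One-sided 95% upper limit, 0 events | Two-sided exact upper limit, 0 events | Chance of ≥1 case at 5% risk |
|---|---|---|---|
| 8 | 31.2% | 36.9% | 33.7% |
| 20 | 13.9% | 16.8% | 64.2% |
| 40 | 7.2% | 8.8% | 87.1% |
| 80 (all) | 3.7% | 4.5% | 98.3% |

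**4. Dilution in the all-dosed percentage.** Suppose the risk is 20% in prolonged and 2% in short infusions (assumed). The pooled rate is share × 20% + (1 − share) × 2%:
- 10% prolonged: 2.0% + 1.8% = 3.8%
- 25% prolonged: 5.0% + 1.5% = 6.5%
- 50% prolonged: 10.0% + 1.0% = 11.0%

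**5. By cohort.** With a 10% share, a cohort of 20 has a chance of 0.9^20 = 12% of containing no prolonged infusion at all. The by-cohort AE tables would look the same in form either way.

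**The case against.** **The endpoint wording is looser than it looks.** The protocol synopsis describes exposure from 30 minutes up to 96 hours, so the endpoint could be read as covering any length. The synopsis and Protocol 10.3.3 tie prolonged-infusion safety to laboratory parameters and put AEs in a separate sentence. This is fair as far as it goes, but Protocol 3.3 and SAP 11 join the two. If the phrase covers any length, the word prolonged does no work and the report should say so.

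**The plan already shows some of this.** SAP 8 reports infusion duration in the safety population, and SAP 4 promises listings of all eCRF data. The 48, 72 and 96 h chemistry summaries draw only on patients in those time windows. This stands as partial mitigation: a reader will see how long patients were infused. The link to AEs would still have to be rebuilt from listings, unplanned.

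**Grouping patients by achieved duration would introduce bias.** This also stands, and it shapes the fix. Duration is a post-baseline variable. Protocol 3.1 allows stopping for safety, and Protocol 4.4 lists an adverse event as a reason to discontinue. An AE at hour 3 that ends the infusion would move that patient out of a 24-hour-or-longer group, which would then hold those who tolerated the first day. Conversely, an event at minute 20 of a 90-hour infusion would count as a prolonged-infusion event.

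**Stronger readings the documents do not support.** A reader might infer that few patients will have prolonged infusions. Nothing gives the share, and SAP 8 lists post-surgical hypertension among the reasons for starting drug. A reader might also infer that AEs are shown over one undivided denominator; the cohort and hypertension splits say otherwise. Nor does the plan claim a 3.7% limit: SAP 11.1 specifies no interval for AEs, and the study is descriptive.

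**Conclusion.** The point holds as a gap between the stated endpoint and the planned analysis. The plan does not secure prolonged exposure, and its AE and SAE incidence is not linked to the exposure obtained. The pooled percentage therefore cannot by itself support a statement about prolonged infusion.

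The size depends wholly on a share that the documents do not give. Under assumed shares of 10% to 50%, the data could exclude only risks above 31% to 7%, against 3.7% if all 80 were so exposed. The dilution figures rest further on assumed event risks.

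The point does not extend to the 48, 72 and 96 h chemistry summaries. It does not show that the trial will lack prolonged exposure, only that it need not have it and that the AE tables would not reveal this.

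**What to change.** 1. **SAP 11.1:** add descriptive tables of TEAEs, SAEs and AEs leading to discontinuation by time of onset since infusion start, for example 0 to <24 h, 24 to <48 h and ≥48 h on drug, and post-infusion through day 7.
   - For each on-drug interval, give the number of patients still on drug at its start, the on-drug patient-hours and an exact 95% upper limit.
   - For the post-infusion interval, use the patients entering follow-up as the denominator and list each event with that patient's infusion duration.
   - Present these overall, and by cohort only where numbers allow.
2. **Beside these tables,** show how many patients reached each duration, from the on-drug duration already derived in SAP 8.
3. **Do not base the conclusion solely on patients who achieved 24 hours or more,** because AEs can end the infusion early.
4. **SAP 11 and Protocol 10.3.3:** state that the all-dosed table describes safety at any exposure, and that statements about prolonged infusion are limited to the exposure actually obtained. The cut-points above are illustrative. The sponsor should fix them in advance and say what prolonged means for the analysis; the nearest usage in the protocol is an adult study described as 72 hours or more (Protocol 1.2.2).

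**Cost:** a few extra tables, no extra patients and no change to dosing. The denominators will be small and the prolonged-infusion statement weaker. The tables need AE onset to clock time. The protocol's AE sections do not appear to specify this, so the sponsor should confirm that the eCRF captures it.
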